ICH	International Conference on Harmonization of Technical Requirements for Registration of Pharmaceuticals for Human Use				
IEC	Independent Ethics Committee				
IMS	Integrated Medical Safety				
i.v.	intravenous(ly)				
IRB	Institutional Review Board				
IVRS	Interactive Voice Response System				
MMF	Mycophenolate mofetil				
MPA	Mycophenolic acid (Refers to mycophenolate sodium EC or mycophenolate mofetil containing products)				
o.d.	once a day				
p.o.	oral(ly)				
REB	Research Ethics Board				
SAE	serious adverse event				

Glossary of terms

Assessment	A procedure used to generate data required by the study
Control drug	A study drug used as a comparator to reduce assessment bias, preserve blinding of investigational drug, assess internal study validity, and/or evaluate comparative effects of the investigational drug
Enrollment	Point/time of patient entry into the study; the point at which informed consent must be obtained (i.e. prior to starting any of the procedures described in the protocol)
Investigational drug	The study drug whose properties are being tested in the study; this definition is consistent with US CFR 21 Section 312.3 and is synonymous with "investigational new drug."
Medication number	A unique identifier on the label of each medication package in studies that dispense medication using an IVR system
Patient number	A number assigned to each patient who enrolls in the study. When combined with the center number, a unique identifier is created for each patient in the study.
Stage	A major subdivision of the study timeline; begins and ends with major study milestones such as enrollment,, completion of treatment, etc.
Period	A minor subdivision of the study timeline; divides phases into smaller functional segments such as screening, baseline, titration, washout, etc.
Premature patient withdrawal	Point/time when the patient exits from the study prior to the planned completion of all study drug administration and assessments; at this time all study drug administration is discontinued and no further assessments are planned
Stop study participation	Point/time at which the patient came in for a final evaluation visit or when study drug was discontinued whichever is later
Study drug	Any drug administered to the patient as part of the required study procedures; includes investigational drug and any control drugs

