Study drug will be dispensed by the Barnes-Jewish Hospital Investigational New Drug (BJH IND) pharmacy, [name] They will receive a supply of 360 tablets of the 0.5 mg strength during their first study visit with a prescription label as outlined below.

Study drug supply, storage and tracking

Study drug supply with be shipped to the IND pharmacy, and it will be stored within an automated dispensing cabinet system (PYXIS), accessible only to the BJH IND pharmacy staff. Dispensing logs will be maintained by the BJH IND pharmacy staff, and the study team will track doses assigned for each patient during and following the titration period.

Instructions for prescribing and taking the study drug

Upon enrollment, patients will be instructed to begin taking 2 tablets by mouth twice daily beginning the evening following enrollment. Patients will continue taking everolimus twice daily through the study duration until the morning of the final visit (visit 6- end of month 12). The dose will be adjusted based on everolimus trough levels (as measured in whole blood using liquid chromatography and mass spectrophotometry methods) to target an everolimus level between 3 and 8 ng/mL. These assessments of everolimus levels will be made on a q2week schedule initially.

Permitted study drug dose adjustments and interruptions

As above, patients will have regular assessments of their everolimus levels. The first level assessment will be taken no sooner than 3 days following administration of the first dose. Any dose changes will lead to follow-up levels no sooner than 3 days following dose adjustment. The trough goal for EVR for the study is between 3 and 8 ng/mL. Levels below 3 ng/mL should result in a dose adjustment equaling double the previous dose. Levels above 8 ng/mL should result in a decrease in dose by 0.25 mg per dose. Changes to dose may also be made at treating physician discretion.

Additionally, tacrolimus levels will be assessed and doses adjusted upon these levels, targeting a trough level between 2 and 5 ng/mL. Adjustments to TAC doses may be made at treating physician discretion.

Drug interruptions may occur at the discretion of treating physician for severe or opportunistic infection, evidence of adverse effects requiring interruption (such as pulmonary infiltrates), or during periods of severe illness where oral route is unavailable.

Other concomitant treatment

Stong inducers or inhibitors of CYP3A4/3A5 are prohibited.

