Visit schedule and assessments

Table 7-1 lists all of the assessments and indicates with an "x" the visits when they are performed. The day of enrollment will be considered to be study Day 1. Subjects will make scheduled study visits on Day 1, at the end of Months 1, 3, 6, and 12. Subjects who discontinue their study treatment regimen should be treated according to standard of care immunosuppression and return for the assessments indicated by X in Table 6-1. If they refuse to return for these assessments or are unable to do so, every effort should be made to contact them or a knowledgeable informant by telephone to determine the subject and graft status.

Table Error! No text of specified style		A550	essment	schedule	;	
	Screening	Treatment period (post-switch)				Final study visit
	And	Month 1	Month 3	Month 6	Month 9	Month 12
	Enrollment		-	•		
Visit	1	2	3	4	5	6
Medical history	Х					
Medication history	Х	Х	Х	Х	Х	Х
Vital signs	Х	Х	Х	Х	Х	Х
Height, weight, BMI	Х	Х	Х	Х	Х	Х
Informed consent	Х					
Dispense medication and/or instruct subject regarding use	X					
Record adverse events	Х	Х	Х	Х	Х	Х
GSRS and GIQLI instruments	Х	Х	Х	Х		Х
Clinical laboratory tests	Х	Х	Х	Х	Х	Х
Tacrolimus/everolimus trough levels	Х	X	Х	Х	Х	Х
**Trough concentrations to be drawn twice weekly upon initiation and/or dosage change until therapeutic goal level is obtained						
Evidence of bacterial, viral, and fungal infection **At the following visits and at any point such infection is reported to a physician, transplant coordinator, or study coordinator	X	X	x	X	X	X

Table Error! No text of specified style in document.-1 Assessment schedule

Patient demographics/other baseline characteristics

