After informed consent has been signed and the subject's eligibility to participate in the study has been determined, baseline subject information will be obtained in accordance with local regulations, including date of birth, age, sex (with child bearing status for females), race and ethnicity. In addition, relevant medical history (including CKD and ESRD history) and current medical conditions at screening, a full physical examination, vital signs and a pregnancy test (for females of child-bearing potential) will also be performed (or documented if recently performed). At Baseline/Transplantation information on the renal transplant procedure, recipient and donor transplant background, recipient and donor viral serology and recipient/donor HLA testing results will be recorded. Post-transplant, when all Inclusion/Exclusion criteria are met, the subject may begin receiving drug.

Treatment exposure and compliance

All pre-transplant immunosuppression administered, such as basiliximab, rATG and any other agents (CNI, MPA and/or corticosteroids) administered pre-enrollment will be recorded. All post-enrollment doses of everolimus and tacrolimus administered during the course of the study will be recorded in the data monitoring sheets. For all these immunosuppressive drugs the start date, total dose, stop date and reason for dose administration or dose change are to be provided. Tacrolimus trough levels will be determined locally and recorded on the data monitoring sheets. The local trough values will be used to adjust the tacrolimus dosing. Everolimus trough levels will be determined by the local laboratory and recorded on the data monitoring sheets.

Efficacy

Gastrointestinal Symptom Rating Scale (GSRS)

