Height will be recorded at Screening only, weight will be recorded at Screening and at each subsequent visit. Results will be recorded in the visit history form.

Laboratory evaluations

All lab work will be conducted at local laboratories, with the exception of study visit laboratories, which will be conducted on-site.

Pregnancy and assessments of fertility

Pregnancy testing (serum) must be carried out for all females of child-bearing potential. A negative serum pregnancy test must be recorded within 30 days of enrollment.

Other assessments

As above

Health-related Quality of Life

As above

Safety monitoring

Adverse events

Definition of an AE: Any untoward medical occurrence in a subject administered a pharmaceutical product that does not necessarily have a causal relationship with the treatment. An AE can therefore be any unfavorable and unintended sign (including an abnormal laboratory finding), symptom, or disease temporally associated with the use of a medicinal (investigational) product, whether or not considered related to the investigational medicinal product.

Investigational Medicinal Product (IMP) includes the drug under evaluation and the comparator drug(s) if specified as part of the research objective, given at any time during the study. Medical conditions/diseases present before starting the drug of interest are only considered adverse events if they worsen after starting the drug of interest.

The occurrence of adverse events will be sought by non-directive questioning of the patient at each visit during the study. Adverse events also may be detected when they are volunteered by the patient during or between visits or through physical examination, laboratory test, or other assessments. All adverse events will be recorded in the study database including the following information:

- 1. the severity grade (mild, moderate, severe) or (grade 1-4) (delete 1 of the 2 options)
- 2. its relationship to the drug(s) of interest (suspected/not suspected)
- 3. its duration (start and end dates or if continuing at final exam)
- 4. whether it constitutes a serious adverse event (SAE)

Serious adverse event reporting

A SAE is any untoward medical occurrence that at any dose:

- results in death,
- is life-threatening,
- requires inpatient hospitalization or prolongation of existing hospitalization,
- results in persistent or significant disability/incapacity,
- is a congenital anomaly/birth defect,
- is otherwise a significant medical event.

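### A woman may start everolimus on a negative pregnancy result about 30 days old, and no entry criterion or dispensing step asks for a current one

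*Combined protocol and SAP*

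**What the plan says.** The provisions sit in several sections of the combined protocol and SAP.

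- **Pregnancy and assessments of fertility.** Serum testing is mandatory for all women of child-bearing potential. The timing rule is "A negative serum pregnancy test must be recorded within 30 days of enrollment". No repeat test is specified.
- **Patient demographics/other baseline characteristics.** The paragraph opens by saying that, after consent and once "eligibility to participate in the study has been determined, baseline subject information will be obtained". It then says "a pregnancy test (for females of child-bearing potential) will also be performed (or documented if recently performed". What counts as recent is not defined there, so the 30 days above is the only numerical limit. The paragraph ends with the release rule: "when all Inclusion/Exclusion criteria are met, the subject may begin receiving drug".
- **Instructions for prescribing and taking the study drug.** On enrolment, "patients will be instructed to begin taking 2 tablets by mouth twice daily beginning the evening following enrollment". Neither this section nor the one on dispensing mentions a pregnancy result.
- **Visit schedule and assessments.** "The day of enrollment will be considered to be study Day 1". The table has a visit 1 row, "Dispense medication and/or instruct subject regarding use", and a row for clinical laboratory tests whose content is not listed. No row names a pregnancy test.
- **Glossary.** Enrolment is "the point at which informed consent must be obtained (i.e. prior to starting any of the procedures described in the protocol".
- **Informed consent procedures.** Women are told of unknown fetal risk. Keeping to contraception is a condition of taking part, and a woman whose compliance is in doubt should not be entered.

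**The concern.** There are two separate gaps.

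The first is the age of the result. A test taken about a month earlier in routine care satisfies the rule. It says nothing about a conception between that test and the switch to everolimus, and no later test is called for before the first dose.

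The second is where the requirement sits. Drug is released when the inclusion and exclusion criteria are met, but those lists do not mention pregnancy. Staff working from the eligibility list, the visit table and the dispensing instructions would find no pregnancy check named in any of them.

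At stake is fetal exposure that a current test could have prevented. The consent section's warning concerns pregnancy arising during the study, but the same worry applies to a pregnancy already present at first dose. The section on pregnancies requires any pregnancy on study drug to be reported within 24 hours and followed to outcome. That records an exposure and does not prevent it.

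**Working it through.** No power or error-rate figure is involved. The check is date arithmetic, a count of criteria, and a comparison of sections.

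**1. Oldest result allowed at first dose**

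Inputs: a window of 30 days (pregnancy-testing section) and a lag from enrolment to the evening dose of 0 to 1 day (prescribing section; the range covers reading the evening as that of Day 1 or of the next day).

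Maximum age = window + lag = 30 + (0 to 1) = 30 to 31 days.

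**2. How much of this comes from counting from enrolment**

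If the same 30 days ran to first dose, the maximum would be 30 days. The difference is 0 to 1 day. Moving the anchor without shortening the window would change almost nothing.

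**3. Which women can have an old result**

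Consent defines enrolment and precedes every study procedure. That leaves two routes:

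| Route | When the test is drawn | Age at first dose |
|---|---|---|
| Drawn for the study at visit 1 | Day 1 | 0 to 1 day |
| Earlier routine-care result documented | Up to 30 days before Day 1 | Up to 30 to 31 days |

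Only the second route gives an old result, and the baseline section expressly allows it. The documents do not say how many women would take each route.

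**4. Whether the release rule covers pregnancy**

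- Full criteria: 4 inclusion + 9 exclusion = 13; 0 name pregnancy.
- Synopsis key criteria: 3 + 9 = 12; 0 name pregnancy.
- Assessment-table rows: 11; 0 name a pregnancy test. This is the weakest of the three counts, because the laboratory row could include one.
- Exclusions judged at the time of possible conversion: numbers 4 to 8, so 5 of 9 (eGFR, proteinuria, blood counts, wound healing, lipids).

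The protocol thus already wants eligibility to be current at the switch for most of its exclusions, while pregnancy status may be a month old.

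**5. How many women**

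The number of women of child-bearing potential is not given. The planned total is 25 in the synopsis and 30 in the population section. Exposures cannot be estimated without assuming both that number and a conception rate, and the documents supply neither.

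**The case against.** The strongest reply is that the plan already protects these women. Testing is mandatory and the recorded result must be negative, and that binds wherever it appears in the protocol. Treating a woman known to be pregnant would breach it. The contraception condition works as an entry bar in substance, though it lies outside the numbered list. The documents also set no standard by which 30 days is too long, and they give no count of women at risk. All of this stands, and it is why the point is minor. It does not close the gap: contraception looks forward, and neither safeguard detects a conception between an earlier negative test and the switch.

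A reader might also infer three stronger things that the documents do not support.

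- *That counting from enrolment is the fault.* It accounts for at most about one day.
- *That the missing criterion makes the result old.* It does not; the two gaps are independent.
- *That the plan permits dosing before any result is back.* The 30-day rule states no direction, and a test drawn for the study must fall on or after the day of consent, so the words can be stretched that far. The reading is strained. The test is mandatory and listed with the baseline work, and the sentence releasing drug comes at the end of that same paragraph. What remains is narrower: no sentence says that the negative result must be on file before dispensing.

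Finally, a single visit 1 test does nothing for pregnancies that begin later in the 12 months of treatment. That is true, and the proposal claims no more.

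**Conclusion.** The concern holds as a minor patient-safety point. Followed as written, the plan lets a woman of child-bearing potential start everolimus on a routine-care result up to about 30 to 31 days old with no repeat. Separately, neither the criteria that release drug nor the dispensing instructions mention a pregnancy result.

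This rests on reading the 30 days as running back from enrolment, which is the natural reading, and on the undefined laboratory row not already including a pregnancy test for every such woman at visit 1. If it does, the practical gap is smaller and the change is mostly one of wording.

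The documents do not support saying that the plan lacks pregnancy safeguards or that women known to be pregnant could be treated. There is no effect on sample size, power or analysis.

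**What to change.** 1. In the pregnancy-testing section, require a serum test drawn with the visit 1 laboratory work for every woman of child-bearing potential, with the negative result on file before study drug is dispensed.
2. In the baseline section, remove the option for an earlier result to replace this test.
3. Add to both exclusion lists: pregnancy, or no negative serum test at the time of possible conversion in a woman of child-bearing potential.
4. In the dispensing and prescribing sections, make supply and the first evening dose conditional on that result.
5. Add a visit 1 pregnancy-test row to the assessment table.

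Item 1 should not be reduced to moving the 30-day window to first dose, which gains at most about a day.

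The cost is amendment wording, one added assay on blood already drawn at visit 1 for women whose earlier result would have been accepted, and a possible short delay to first dose while the result is awaited.

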Study drug discontinuation	Point/time when patient permanently stops taking study drug for any reason; may or may not also be the point/time of premature patient withdrawal
Variable	Information used in the data analysis; derived directly or indirectly from data collected using specified assessments at specified timepoints

Protocol synopsis

Title of study: Conversion from MPA to Zortress (everolimus) for GI toxicity post-renal transplantation

This study is a prospective, single-center study to evaluate the effectiveness of conversion from MMF or EC-MPS to EVR during the first year post-renal transplant in patients who experience gastrointestinal adverse effects. The primary outcome will be change in GSRS from baseline (time of conversion) to 30 days post-conversion.

In total, 25 patients will be enrolled and converted from MPA to EVR, at an initial dose of 1 mg PO BID with target everolimus troughs between 3 - 8 ng/mL. Patients who are less than one year from date of transplant with identified GI symptoms who are on immunosuppression with tacrolimus, MPA, and prednisone will be enrolled and followed for 1 year. These patients will be compared to an historical cohort of patients receiving azathioprine for safety outcomes (including rejection and graft/patient survival).

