- 2. Presence of a preexisting significant GI condition that does not have a presumed causal relationship with MPA

- 3. Evidence of any GI disorder induced by an infection, underlying medical condition, or concomitant medication other than MPA
- 4. eGFR<35 ml/min at time of possible conversion
- 5. Proteinuria >1 gram/day at time of possible conversion
- 6. Profound bone marrow suppression at the time of possible conversion as defined as:
 - Hemoglobin <10 g/dL
 - WBC <3 K/cumm
 - Platelets <100 K/cumm
- 7. Wound healing issues at time of possible conversion (eg, wound dehiscence, wound infection, incisional hernia, lymphocele, seroma)
- 8. Elevated total cholesterol (>350 mg/dL) and/or triglycerides (>500 ng/dL) at time of possible conversion
- 9. Hypersensitivity to everolimus, sirolimus, or other rapamycin deriviatives

Investigational and reference therapy:

Investigational therapy

- Everolimus tablets 0.25 mg, 0.5 mg, and/or 0.75 mg

Study design: Patients will be selected if they experience non-infectious GI adverse effects within the first 12 months post transplant. Following selection they will have a baseline screening and enrollment with a complete medical history, medication history, vital signs and labs (including tacrolimus and everolimus levels). In addition, their adverse effects and GSRS and GIQLI will be recorded. After enrollment they will have medication history, vitals, labs (including tacrolimus), and GSRS/GIQLI and adverse events recorded at months 1, 3, 6, 9, and 12 (excepting GSRS and GIQLI at month 9).

Efficacy assessments:

- Change in GSRS from baseline to month 3
- Change in GSRS subscores from baseline to month 3
- Changes in GSRS from basline to month 6 and 12
- Change in GIQLI from baseline to month 3
- Change in GIQLI subscores from baseline to month 3
- Changes in GIQLI from baseline to month 6 and 12

Other assessments:

- BPAR rates during study (compared with historical control)
- eGFR by MDRD4 from baseline to month 12 (compared to historical control)
- Death (compared with historical control)
- Graft loss (compared with historical control)

Data analysis:

Data for primary and secondary efficacy will be compared using a paired T-test.

Background

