This study will be conducted over a 2-year period, during which patients will be enrolled through the first year, and follow-up of a minimum of 1 year will be collected on each patient. Interim analyses will be conducted at 6-months or upon enrollment of 15 patients (whichever is earliest). The interim analyses will assess the rate of study drug discontinuation due to non-efficacy (as determined by nephrologist). If more than 5 patients (33%) have discontinued drug due to non-efficacy, the study will be terminated. Additionally, any other problems or safety signals will be addressed by the research team at this time.

Subjects meeting criteria will be asked to sign an informed consent, and upon execution of informed consent this will be considered study day 1. They will examined on study day 1 including a medical history, medication history, vital signs, height, weight, and BMI. Subjects will complete GSRS and GIQLI surveys, report adverse effects, and complete laboratory tests, including tacrolimus levels. Subjects will have 5 additional visits during the study period, which will include a medication history, vital signs, height/weight/BMI, adverse effect recording, GSRS and GIQLI (excepting visit 5), laboratory work including tacrolimus and everolimus levels, and reporting of infectious symptoms. These visits will occur at the end of months 1, 3, 6, 9, and 12.

Figure Error! No text of specified style in document.-1 St

Study design

Population

We intend to include patients who have received kidney transplant at the Washington University/Barnes-Jewish Hospital transplant program in the year prior to enrollment who are exhibiting signs of non-infectious GI toxicity determined by the treating physician to be secondary to MPA. In total, 30 candidates will be enrolled and treated with conversion from MPA to EVR. We anticipate a dropout rate of 20%, and expect that 24 patients will complete a full year of study drug. Severity of GI adverse effects will be assessed using the GSRS and GIQLI scales, but no specific severity threshold will be used to enroll patients. The study will be conducted largely on outpatients, but patients may be initially enrolled during inpatient stays.

Inclusion criteria

Patients eligible for inclusion in this study have to fulfill all of the following criteria:

- 1. Patients must give written informed consent before any assessment is performed.

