Data collection will occur via the RedCap system. All local staff have received training on RedCap. Multiple forms will be created, including a baseline/screening form, and visit-specific forms. Only investigators will have access and the ability to download data.

Database management and quality control

The principal investigator will take responsibility for assessing quality data entry by overseeing all data entry into the RedCap system.

Data analysis (Any or all sections may be included based on type of study)

Statistical analysis and report writing will be performed when the last subject has completed 12 months on study.

Populations for analysis

Subjects completing three months of therapy and returning for study visit #2 will be included in the primary analysis. All subjects receiving at least one dose of everolimus will be included in all outcomes related to safety.

Patient demographics/other baseline characteristics

Demographic and background information for the population will be summarized using frequency distribution (for categorical variables) and descriptive statistics of mean, median, maximum, minimum and standard deviation (for continuous variables).

Treatments (study drug, rescue medication, other concomitant therapies, compliance)

The number of patients remaining on study medication at each study visit will be recorded. Additionally, mean tacrolimus and everolimus levels will be reported at each study visit.

Analysis of the primary objective(s)

Variable

The primary variable is the resultant score derived from the GSRS, which ranges from 0 - 45, compared at enrollment and at visit 2 (end of month 3).

Statistical hypothesis, model, and method of analysis

The null hypothesis: Conversion from MPA-based immunosuppression to EVR-based immunosuppression will result in similar GSRS scores at 3 months compared to baseline.

We will analyze changes in the GSRS using a paired T-test.

Handling of missing values/censoring/discontinuations

We will not include patients in the primary analysis and subsequent analyses of efficacy if they drop out of the study. We will analyze safety endpoints from a modified ITT approach, whereby patients receiving at least one dose of everolimus are considered on therapy until the end of their study period (12 months).

Supportive analyses

A per-protocol set will be analyzed as a secondary endpoint with regards to safety endpoints, including BPAR, graft loss, and death.

Analysis of secondary objectives

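### The primary GSRS endpoint is set at month 1 in some places and month 3 in others, and its visit number contradicts the visit schedule

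*Combined protocol and SAP*

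**What the plan says.** The time point of the primary endpoint appears in five places.

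- Synopsis, opening text: "The primary outcome will be change in GSRS from baseline (time of conversion) to 30 days post-conversion".
- Synopsis, efficacy assessments: the list opens with "Change in GSRS from baseline to month 3". It goes on to months 6 and 12 and contains no 30-day change.
- Section 10.1, Populations for analysis: "Subjects completing three months of therapy and returning for study visit #2 will be included in the primary analysis".
- Section 10.4.1, Variable: the GSRS score is "compared at enrollment and at visit 2 (end of month 3".
- Section 10.4.2, Statistical hypothesis: under the null, conversion "will result in similar GSRS scores at 3 months compared to baseline".

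On timing, the Study design section says "Subjects will have 5 additional visits during the study period" after study day 1, and "These visits will occur at the end of months 1, 3, 6, 9, and 12". The assessment schedule numbers enrollment as visit 1 and month 1 as visit 2. GSRS is administered at both month 1 and month 3.

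**The concern.** The instrument (GSRS), the comparison (within-patient change from baseline) and the test (paired t-test) are fixed. The time point is not. An analyst who follows the visit number in 10.1 and 10.4.1 takes the month 1 score, in line with the synopsis sentence. One who follows the month named in 10.4.1 and 10.4.2 takes the month 3 score. Each can cite the plan.

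There is little to prevent a choice made after the event. The study is open-label, analysts included. Investigators conduct the GSRS interviews and can download the data. The analysis is run only after the last patient's month 12, when both results exist. If the more favourable of the two can be called primary, the 0.05 level no longer holds.

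The analysis set is affected as well. Section 10.1 joins a three-month therapy condition to a one-month visit, so it fits neither endpoint.

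**Working it through.** **1. Visit numbers against months**

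| Visit | Time | GSRS collected |
|---|---|---|
| 1 | Enrollment | yes |
| 2 | End of month 1 | yes |
| 3 | End of month 3 | yes |
| 4 | End of month 6 | yes |
| 5 | End of month 9 | no |
| 6 | End of month 12 | yes |

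Three other places confirm this numbering, so it does not depend on how the table was read from the PDF:

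- The dosing instructions give the final visit as "visit 6- end of month 12".
- The survey-free visit is month 9 in the synopsis and visit 5 in the Study design section.
- Section 10.5.1 analyses GIQLI at visits 2, 3, 4 and 6, which are the four follow-up survey visits in the table.

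Visit 2 is therefore month 1, and the definition in 10.4.1 contradicts itself.

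**2. Which time point each statement supports**

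| Statement | Month 1 | Month 3 |
|---|---|---|
| Synopsis, primary outcome | x | |
| Synopsis, efficacy list | | x |
| 10.1, three months of therapy | | x |
| 10.1, visit number | x | |
| 10.4.1, visit number | x | |
| 10.4.1, month in brackets | | x |
| 10.4.2, null hypothesis | | x |

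**3. Whether the sample size settles it**

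Inputs from section 10.6: change 12, SD 18 (taken as the SD of the change), significance level 0.05 (taken as two-sided; the text does not say), power 80%, dropout 20%.

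- Standardised change: 12/18 = 0.667.
- Paired t-test with the noncentral t distribution, noncentrality √n × 0.667. At n = 20 this is 2.98 and power is 80.7%.
- Enrolled: 20/(1 − 0.20) = 25, which reproduces the plan's figure.

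No time point enters this calculation. The 25 fits month 1 and month 3 equally well and cannot show which was meant.

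**4. Error rate if either time point could count**

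- If the two tests were independent: 1 − 0.95² = 9.75%.
- They are correlated, because both changes come from the same patients and share a baseline. The documents give no correlation, so a range is assumed.
- Simulation: two paired t-tests under no true change, each at two-sided 0.05, n = 24 (30 × 0.80, the expected completers in the Population section).

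| Assumed correlation of the two changes | At least one p < 0.05 |
|---|---|
| 0.3 | 9.5% |
| 0.5 | 9.1% |
| 0.7 | 8.5% |
| 0.8 | 7.9% |
| 0.9 | 7.1% |

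With n = 20 (25 × 0.80) the results agree to within about 0.1 percentage point.

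**5. Effect on who is analysed**

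- A patient who attends visit 2 and stops everolimus before month 3 has a month 1 score but fails the therapy condition.
- A patient who completes three months of therapy and attends visit 3 but missed visit 2 has a month 3 score, yet 10.1 read literally excludes that patient.
- A patient who meets both parts of 10.1 may still have missed visit 3 and have no month 3 score.

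**6. Cost of keeping both time points**

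With a Bonferroni split at 0.025 each, 80% power per test needs 24 evaluable patients, and 24/0.80 = 30 enrolled. With 20 evaluable, power per test falls to 70.6%.

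**The case against.** The best defence is that this is a slip in a label. Four statements point to month 3 in words, and only one sentence says 30 days. On that reading the synopsis sentence and the two visit numbers are the errors, and a sensible analyst would use month 3. There are also only two real time points, since the wording in 10.4.1 mixes them and does not add a third.

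The count of time points is right, and month 3 is indeed better supported. But the visit number occurs twice in the primary analysis text and agrees with the 30 days in the synopsis, so it cannot be set aside as an isolated typing error. Nor does visit 2 mean the second visit after enrollment, because section 10.5.1 uses the schedule's own numbering.

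The error rate is open to fair qualification:

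- It applies only if someone picks the more favourable visit. Nothing in the documents shows that intention.
- With equal variances and equal correlations between visits, the shared baseline alone makes the correlation of the two changes (1 − ρ)/(2(1 − ρ)) = 0.5. It is higher if months 1 and 3 resemble each other more than they resemble baseline. The lower half of the error range, about 7% to 9%, is therefore more plausible than the top.
- The figure counts significant worsening as well as improvement. For false claims of improvement alone it is about half: roughly 4.0% to 4.8% for correlations of 0.8 to 0.3, against 2.5%.

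These points moderate the size of the problem. They do not remove the contradiction.

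**Conclusion.** The concern holds. The documents define the primary endpoint at two different times, identify one of them by the wrong visit number, and do not say which text governs. Until that is settled, the plan does not determine a single primary result or the patients who contribute to it.

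The inflation is from 5% to about 7.9% to 9.5%, on these assumptions: two-sided tests, either time point allowed to count, 20 to 24 evaluable patients, and a correlation of 0.8 to 0.3 between the changes. It is a risk created by the ambiguity and not evidence of any intended selection. The point must be fixed before any GSRS change is analysed.

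**What to change.** Name one primary endpoint throughout. The choice is the sponsor's. The better-supported option is the change in total GSRS from visit 1 to visit 3 (end of month 3), which agrees with the null hypothesis, the synopsis efficacy list and the three-month condition.

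- Sections 10.1 and 10.4.1: replace the reference to visit 2 with visit 3.
- Synopsis: change the primary outcome sentence from 30 days to month 3.
- Synopsis efficacy list and section 10.5.1: add the 30-day (visit 2) change in total GSRS as a secondary endpoint.
- Section 10.6: state the time point to which the 12-point change refers, and that the 0.05 level is two-sided if that is intended.

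If the sponsor prefers month 1, more has to change: the null hypothesis, the month in 10.4.1 and the efficacy list. The three-month therapy condition in 10.1 would also have to be reconsidered, because it would drop patients with valid month 1 scores according to what happened to them later.

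With month 3, the cost is a wording amendment. Both assessments are already scheduled, and the sample size calculation stays at 20 evaluable and 25 enrolled. Date the amendment before any look at the GSRS changes.
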